### 6.1.1 Dosing regimen

All eligible patients will be randomized starting from Cycle 1 Day 1 to receive either:

- Fulvestrant + ribociclib
- Fulvestrant + placebo

Ribociclib or placebo will be given orally once daily on days 1-21 of each 28 day cycle. Days 22-28 will be a “rest” period from dosing with ribociclib or placebo.

Fulvestrant will be administered intramuscularly into the buttocks slowly (1-2 minutes per injection) as two 5 mL injections, one in each buttock, on Cycle 1 Day 1 (C1D1), Cycle 1 Day 15 (C1D15), Cycle 2 Day 1 (C2D1) and every 28 days thereafter (i.e., the first day of each 28 day cycle) as per the (FASLODEX® [prescribing information](#)). There will be no “rest” in the fulvestrant schedule.

**Table 6-1 Dose and treatment schedule**

Study treatments	Pharmaceutical form and route of administration	Dose	Frequency and/or Regimen
fulvestrant	Two 5ml injections for i.m. administration	500 mg	Dosed every 28 days (Cycle n Day 1) with 1 additional dose on Day 15 of Cycle 1
ribociclib/placebo	Capsule for oral use	600 mg	Once daily; days 1 to 21 in a 28-day Cycle

[figure not shown]
The study drugs will be administered as a flat-fixed dose and not by body weight or body surface area. There shall be no breaks between dosing cycles. A complete cycle of treatment is defined as 28 days. All study treatment drugs should be administered as described below in [Section 6.1.1.1](#) and [Section 6.1.1.2](#).

The investigator or responsible site personnel will instruct the patient to take the study drugs as per protocol (promote compliance). Patients will be instructed to return unused study drugs to the site at discontinuation or completion of treatment. The site personnel will ensure that the appropriate dose of each study drug is administered and that the drug accountability is performed.

#### 6.1.1.1 General dosing guidelines

The study treatments should be taken as follows:

- On scheduled visit days, patients must take study treatments in the clinic under the supervision of the Investigator or designee. On all other days patients will take ribociclib/placebo at home.
- Patients should be instructed to take the study treatment of ribociclib/placebo capsules together with a large glass of water (~250 mL or ~8 oz) once a day at the same time each day. For the first cycle, patients must take ribociclib/placebo in the morning due to PK assessments. Once the PK assessments have been completed, patients can determine if

they prefer am or early afternoon dosing but should maintain a consistent time regardless of am or early afternoon dosing. Evening doses are strongly **not recommended**.

- In general, study treatment may be taken without regard to meals. Please see [Section 6.1.1.2](#) below for additional guidelines for fasting lab assessments and for sparse PK collection.
- Patients will be instructed to swallow the capsules whole and not to chew, crush or open them.
- If vomiting occurs during the course of treatment, no re-dosing of the patient is allowed before the next scheduled dose. The occurrence and frequency of any vomiting during a treatment cycle must be noted in the adverse events section of the eCRF. Refer to [Section 6.6.1.4](#) for use of anti-emetic medications.
- Any doses that are missed (not taken within 6 hours of the intended time) should be skipped and should not be replaced or made up on a subsequent day.
- Patients must avoid consumption of grapefruit, grapefruit hybrids, pomelos/pummelos, starfruit, Seville oranges or products containing their juice during the entire study and preferably for an additional 7 days before the first dose of study medications. These foods are known as CYP3A4 inhibitors and have a potential to increase exposure to ribociclib. Orange juice is allowed.
- Herbal or dietary supplements known as strong inhibitors or inducers of CYP3A4/5 or those with a known risk of QT prolongation are not permitted.
- Multivitamins are permitted.

#### **6.1.1.2 Additional guidelines for fasting lab assessments and sparse PK**

##### **Fasting considerations for lab assessments (e.g. glucose and lipid profile)**

- The patient should be fasting overnight (i.e., at least 8-12 hours prior to the blood collection) for all visits with fasting glucose, lipid profile sampling [REDACTED]
- Water is allowed during all fasting periods; however coffee, tea and juice are not permitted during the fasting period.

##### **Meal considerations for sparse PK collection**

- Only for the sparse PK group, the meal condition (fasting, low fat, high fat) must be recorded on the eCRF **within ± 30 minutes of the dose** on C1D15 and C2D15. The meal condition is an estimate; however guidance is provided below.
- On C1D15 and C2D15, when PK is paired with ECG assessments, patients may consume breakfast only after fasted pre-dose blood samples (fasting glucose, fasting lipid profile) have been collected.
- Pre-dose PK should be collected approximately 24 hrs after the last dose (± 2 hrs) and immediately before the next dose.
- A high-fat meal typically contains 800-1000 calories with approximately 50% of the calories coming from fat (500-600 calories) (FDA Guidance for Industry for Food-effect Bioavailability and Fed Bioequivalence Studies, December 2002). An example of a high-

fat meal could be two eggs, 2 slices of bread, 1 tablespoon butter, 1 tablespoon jelly, 3 strips of bacon, 4 ounces of hash brown potato, and 8 ounces of whole milk. A low-fat meal could be approximately 300-500 calories with approximately 25% of the calories coming from fat (75-125 calories) and could include 2 slices of bread, 1 tablespoon light fat margarine, 1 tablespoon jelly, and 8 ounces of skim milk ([USDA National Nutrient Database for Standard Reference, 2010](#)).

### **6.1.1.3 Fulvestrant dosing**

Fulvestrant 500 mg will be given after randomization at Cycle 1 Day 1, at Cycle 1 Day 15 (with a  $\pm 3$  day window) and then at Day 1 of each subsequent cycle during the randomized treatment phase (with  $\pm 3$  day window). Fulvestrant is administered intramuscularly into the buttocks slowly as two 5mL injections, one in each buttock. No dose modification of fulvestrant is planned in this study.

For information on fulvestrant and management of related adverse events, refer to the FASLODEX® SmPC or local Prescribing Information.

### **6.1.2 Guidelines for continuation of treatment**

For guidelines for continuation of treatment, refer to [Section 6.5](#) Dosing modification.

Patients who permanently discontinue fulvestrant for any reason must discontinue ribociclib/placebo, and move to End of Treatment phase, but will remain on study for follow-up evaluations (i.e. tumor follow-up and patient reported outcomes). Patients who permanently discontinue ribociclib/placebo may continue on the study on fulvestrant per investigator's discretion and will continue to be followed for safety and/or efficacy.

### **6.1.3 Ancillary treatments**

Not applicable.

### **6.1.4 Rescue medication**

[figure not shown]
Not applicable.

### **6.1.5 Treatment duration**

Patients will be treated until disease progression (radiologically documented according to RECIST 1.1) or until discontinuation of study treatment due to any other reason (see [Section 7.1.5](#)).

## **6.2 Dose escalation guidelines**

Not applicable

## **6.3 Patient numbering, treatment assignment or randomization**

### **6.3.1 Patient numbering**

Each patient is identified in the study by a Subject Number (Subject No.) that is assigned when the patient is first enrolled for screening and is retained as the primary identifier for the patient throughout his/her entire participation in the trial. The Subject No. consists of the Center Number (Center No.) (as assigned by Novartis to the investigative site) with a sequential patient number suffixed to it, so that each subject is numbered uniquely across the entire database. Upon signing the informed consent form, the patient is assigned to the next sequential Subject No. available to the investigator through the Oracle Clinical RDC interface at that location.

The investigator or designated staff will contact the IRT and provide the requested identifying information for the patient to register them into the IRT. Once assigned, the Subject No. must not be reused for any other subject and the Subject No. for that individual must not be changed, even if the patient is re-screened. If the patient fails to be randomized or start treatment for any reason, the reason will be entered into the Screening Disposition page.

IRT must be notified within 2 days that the patient was not randomized.

### **6.3.2 Treatment assignment or randomization**

Patients will be randomized to one of the **two** treatment arms ([Section 4.1](#) and [Section 6.1](#)) in a ratio of 2:1.

Randomization will be stratified by the following factors:

1. Lung or liver metastases: (yes versus no)
2. Previous endocrine therapy

The randomization numbers will be generated using the following procedure to ensure that treatment assignment is unbiased and concealed from patients and investigator staff. A patient randomization list will be produced by the Interactive Response Technology (IRT) provider using a validated system that automates the random assignment of patient numbers to randomization numbers. These randomization numbers are linked to the different treatment arms, which in turn are linked to medication numbers. A separate medication randomization list will be produced by or under the responsibility of Novartis Global Clinical Supply (GCS) using a validated system that automates the random assignment of medication numbers to medication packs containing each of the study treatments.

Prior to dosing, all patients who fulfill all inclusion/exclusion criteria will be randomized via IRT to one of the treatment arms. The investigator or his/her delegate will call or log on to the IRT and confirm that the patient fulfills all the inclusion/exclusion criteria. The IRT will assign a randomization number to the patient, which will be used to link the patient to a treatment arm and will specify a unique medication number for the first package of study treatment to be dispensed to the patient. The randomization number will not be communicated to the caller.

Following protocol amendment 4, patients will be unblinded to their treatment allocation.

Additionally, patients who are currently allocated to the placebo combination arm and still on study treatment, will be given the opportunity to transition to the LEE011 combination.

Those patients on the placebo arm who do not wish to cross-over from placebo to LEE011 can remain on their current treatment allocation (i.e. fulvestrant alone).

All of the study treatment cross-over registration and dispensing will be managed by the study IRT system. After transition to the investigational treatment, placebo dispensing in IRT will stop. Comparator treatment (i.e. fulvestrant) will continue to be managed locally.

### **6.3.3 Treatment blinding**

This is a double blind study. In particular, patients, investigators, study team, or anyone involved in the study conduct will remain blinded to the identity of the treatment from the time of randomization until database lock. The local (or Novartis-designated) radiologists will remain blinded to the identity of the treatment from the time of randomization until final database lock.

Randomization data are kept strictly confidential until the time of unblinding, and will not be accessible to anyone involved in the conduct of the study. The identity of the treatments will be concealed by the use of investigational drugs (ribociclib or ribociclib matching placebo) that are identical in packaging, labeling, schedule of administration and in appearance. Confidentiality of randomization data is required to limit the occurrence of potential bias arising from the influence that the knowledge of treatment may have on the recruitment and allocation of patients.

Unblinding of study drug assignment will only occur in the case of patient emergencies ([Section 8.3](#)), for regulatory reporting purposes and at the conclusion of the study.

In rare cases when unblinding occurs because of emergency patient management, the actual treatment arm will not be communicated to any of the Novartis employees involved in running the trial in order to remain blinded.

An independent statistical group (external to Novartis), not involved in the trial conduct, will prepare data reports for the DMC. An independent clinical pharmacologist will analyze the data from patients with PK sampling if the data were to be presented at the DMC meetings. Details will be presented in the DMC charter.

Prior to the release of protocol amendment 4, the study met both its primary and secondary endpoints. Given the demonstrated survival benefit from LEE011 treatment, patients will be unblinded to their treatment allocation.

## **6.4 Study drug preparation and dispensation**

Patients will be provided with an adequate supply of study drug for self-administration at home, including instructions for administration, until at least their next scheduled study visit. Patients will receive ribociclib/placebo on an outpatient basis. The investigator shall provide the patient with instructions for ribociclib/placebo administration according to the protocol.

Fulvestrant should be dispensed according to local prescribing information and practice.

The investigator or responsible site personnel must instruct the patient or caregiver to take the study treatment as per protocol. Study treatment will be dispensed to the patient by authorized

site personnel only. All dosages prescribed to the patient and all dose changes during the study must be recorded on the Dosage Administration Record CRF.

### 6.4.1 Study drug packaging and labeling

The study medication packaging has a 2-part label. A unique medication number is printed on each part of this label which corresponds to one of the treatment arms and a [specific visit or dose/dose level]. Responsible site personnel will identify the study treatment package(s) to dispense to the patient by using the IRT and obtaining the medication number(s). Site personnel will add the patient number on the label. Immediately before dispensing the package to the patient, site personnel will detach the outer part of the label from the packaging and affix it to the source document (Drug Label Form) for that patient’s unique patient number.

Medication labels will be in the local language and comply with the legal requirements of each country. They will include storage conditions for the drug and the medication number but no information about the patient.

**Table 6-2 Packaging and labeling**

Study treatments	Packaging	Labeling (and dosing frequency)
ribociclib or placebo	Capsules in bottles	Labeled as ‘LEE011/placebo’  Study treatment packaging has a 2-part label.  A unique medication number is printed on each part of this label which corresponds to one of the two treatment arms.
fulvestrant	Refer to local product information	Refer to local product information

### 6.4.2 Drug supply and storage

Study treatments must be received by designated personnel at the study site, handled and stored safely and properly, and kept in a secured location to which only the investigator and designated site personnel have access. Upon receipt, the study treatment should be stored according to the instructions specified on the drug labels and in the [ribociclib Investigators Brochure].

Study treatments will be procured locally according to local practice and regulation, or supplied by Novartis (or its designee).

### 6.4.3 Study drug compliance and accountability

#### 6.4.3.1 Study drug compliance

Compliance will be assessed by the investigator and/or study personnel at each patient visit and information provided by the patient and/or caregiver will be captured in the Drug Accountability Form. This information must be captured in the source document at each patient visit.

Compliance will be assured by administrations of the study treatment under the supervision of investigator or his/her designee, and will be verified by determinations of ribociclib in plasma.

### **6.4.3.2 Study drug accountability**

The investigator or designee must maintain an accurate record of the shipment and dispensing of study treatment in a drug accountability log. Drug accountability will be noted by the field monitor during site visits and at the completion of the study. Patients will be asked to return all unused study treatment and packaging on a regular basis, at the end of the study or at the time of study treatment discontinuation.

At study close-out, and, as appropriate during the course of the study, the investigator will return all used and unused study treatment, packaging, drug labels, and a copy of the completed drug accountability log to the Novartis monitor or to the Novartis address provided in the investigator folder at each site.

### **6.4.3.3 Handling of other study treatment**

Not applicable.

### **6.4.4 Disposal and destruction**

The study drug supply can be destroyed at the local Novartis facility, Drug Supply group or third party, as appropriate. Study drug destruction at the investigational site will only be permitted if authorized by Novartis in a prior agreement and if permitted by local regulations.

## **6.5 Dose modifications**

### **6.5.1 Dose modification and dose delay**

For patients who do not tolerate the protocol-specified dosing schedule, dose adjustments are permitted in order to allow the patient to continue the study treatment. These changes must be recorded on the Dosage Administration Record CRF.

#### **6.5.1.1 Fulvestrant**

The established clinical dose of fulvestrant (500 mg) will be used in each arm and no dose modification of fulvestrant is planned in this study ([Table 6-3](#)). For information on fulvestrant and management of related adverse events, refer to the FASLODEX® SmPC or local Prescribing Information.

#### **6.5.1.2 Ribociclib/placebo**

Recommendations for dose reduction, interruption or discontinuation of ribociclib in the management of study drug related adverse reactions are summarized in [Table 6-4](#), [Table 6-5](#), [Table 6-6](#), [Table 6-7](#) and [Table 6-8](#). No dose modification for fulvestrant is permitted.

**Table 6-3 Dose modification guidelines**

	Ribociclib/placebo ( 3 weeks on/1 week off schedule)		Fulvestrant	
	Dose	Number of capsules & strength	Dose	Number of injections & strength
Starting dose	600 mg	3 x 200 mg capsules	500 mg	2 x 250mg (5 mL) injections
First dose reduction	400 mg	2 x 200 mg capsules	No dose modification allowed	
Second dose reduction	200 mg	1 x 200 mg capsules	No dose modification allowed	

Clinical judgment of the treating physician should guide the management plan of each patient based on individual benefit/risk assessment. However, for events requiring a discontinuation in [Table 6-4](#), [Table 6-5](#), [Table 6-6](#), [Table 6-7](#) and [Table 6-8](#) or listed in [Section 7.1.3](#), treatment must be discontinued.

Unscheduled local laboratory assessments may be performed if medically indicated to document a (potential) adverse event or when the treating physician cannot wait for central laboratory results for decision making (e.g. dose modifications). In this particular situation, if possible, the blood sample obtained at the same time point should be submitted to the central laboratory for analysis in parallel with local analysis.

The results of the local laboratory will be recorded in the eCRF if any of the following criteria are met:

[figure not shown]
- A treatment decision was made based on the local results, or
- Local lab results document an adverse event not reported by the central lab, or
- Local lab results document an adverse event severity is worse than the one reported by the central lab, or
- There are no concomitant central results available.

**For assessment of patients’ eligibility to the study, only laboratory results from the central laboratory will be used.**

**Table 6-4 Ribociclib/Placebo dose adjustment and management recommendations for hematological adverse reactions (CTC AE v4.03)**

**The results of the local laboratory will be recorded in the eCRF if any of the following criteria are met:**

Toxicity/Grade	Dose Adjustment and Management Recommendations
Thrombocytopenia	
Grade 1 (≥75 x 10  /L)	No dose adjustment required.
Grade 2 (≥50 x 10  /L – <75 x 10  /L)	Dose interruption until recovery to grade ≤1. Re-initiate ribociclib/placebo at the same dose.
Grade 3 (≥25 x 10  /L - <50 x 10  /L)	Dose interruption until recovery to grade ≤1. Re-initiate ribociclib/placebo at the same dose level. If toxicity recurs at grade 3: temporary dose interruption until recovery to grade ≤1 and reduce ribociclib/placebo to the next lower dose level.

Toxicity/Grade	Dose Adjustment and Management Recommendations
Grade 4 (<25 x 10  /L)	Dose interruption until recovery to grade ≤1. Re-initiate ribociclib/placebo at the next lower dose level. If toxicity recurs at grade 4: discontinue ribociclib/placebo.
Absolute neutrophil count (ANC)	
Grade 1 (≥1.5 x 10  /L)	No dose adjustment required.
Grade 2 (≥1.0 - <1.5 x 10  /L)	No dose adjustment required.
Grade 3 (≥0.5 - <1.0 x 10  /L)	Dose interruption until recovery to ≥1.0 x 10  /L. Re-initiate ribociclib/placebo at the same dose level. If toxicity recurs at grade 3: temporary dose interruption until recovery to ≥ 1.0 x 10  /L. If resolved in ≤7 days, then maintain dose level. If resolved in >7 days, then reduce ribociclib/placebo dose to the next lower dose level.
Grade 4 (<0.5 x 10  /L)	Dose interruption until recovery to ≥ 1.0 x 10  /L. Re-initiate ribociclib/placebo at the next lower dose level. If toxicity recurs at grade 4: temporary dose interruption until recovery to ≥1.0 x 10  /L and reduce ribociclib/placebo at the next lower dose level.
Febrile neutropenia	
Grade 3 ANC <1.0 x 10  /L with a single temperature of >38.3 °C (101 °F) or a sustained temperature of ≥38 °C (100.4 °F) for more than one hour	Dose interruption until improvement of ANC ≥ 1.0 x 10  /L and no fever. Restart at the next lower dose level. If febrile neutropenia recurs, discontinue ribociclib/placebo.
Grade 4 Life-threatening consequences; urgent intervention indicated	Discontinue ribociclib/placebo.
Anemia (Hemoglobin)	
Grade 1 (≥10.0 – LLN g/dL)	No dose adjustment required.
Grade 2 (≥8.0 – <10.0 g/dL)	No dose adjustment required.
Grade 3 (<8.0 g/dL)	Dose interruption until recovery to grade ≤ 2. Re-initiate ribociclib/placebo at the same dose.
Grade 4 Life-threatening consequences; urgent intervention indicated	Discontinue ribociclib/placebo.

**Table 6-5 Ribociclib/placebo dose adjustment and management recommendation for hepatic toxicities (CTC AE v4.03)**

Please refer to [Section 6.5.1.2.1](#) for additional information.

HEPATOTOXICITY (BILIRUBIN, SGPT/ALT, SGOT/AST)	
TOTAL BILIRUBIN without ALT/AST increase above baseline value	
Grade 1 (> ULN – 1.5 x ULN) (confirmed 48-72h later)	Maintain dose level with LFTs monitored bi-weekly.
Grade 2 (> 1.5 – 3.0 x ULN)	Dose interruption of ribociclib/placebo If resolved to ≤ grade 1 in ≤ 21 days, then maintain dose level If resolved to ≤ grade 1 in > 21-28 days or toxicity recurs, then reduce 1 dose level Repeat liver enzyme and bilirubin tests twice weekly for 2 weeks after dose resumption

	If toxicity recurs after two dose reductions, or recovery to $\leq$ grade 1 is $> 28$ days, discontinue ribociclib/placebo
Grade 3 ( $> 3.0 - 10.0 \times \text{ULN}$ )	Dose interruption of ribociclib/placebo, until resolved to $\leq$ grade 1, then lower 1 dose level of ribociclib/placebo Repeat liver enzyme and bilirubin tests twice weekly for 2 weeks after dose resumption  If resolved to $\leq$ grade 1 in $> 28$ days or toxicity recurs, discontinue ribociclib /placebo
Grade 4 ( $> 10.0 \times \text{ULN}$ )	Discontinue ribociclib/placebo

Confounding factors and/or alternative causes for increase of total bilirubin should be excluded before dose interruption/reduction. They include but are not limited to: evidence of liver metastases, evidence of obstruction, such as elevated ALP and GGT typical of gall bladder or bile duct disease, hyperbilirubinemia due to the indirect component only (i.e. direct bilirubin component <math>\leq 1 \times \text{ULN}</math>) due to hemolysis or Gilbert Syndrome, other pharmacologic treatment, viral hepatitis, alcoholic or autoimmune hepatitis, other hepatotoxic drugs. For patients with Gilbert Syndrome, these dose modifications apply to changes in direct bilirubin only. Bilirubin will be fractionated if elevated.
	
AST or ALT	
AST or ALT without bilirubin elevation <math>> 2 \times \text{ULN}</math>	
Same grade as baseline or increase from baseline grade 0 to grade 1 (confirmed 48 – 72 h later)	No dose adjustment required with LFTs monitored per protocol if same grade as baseline or bi-weekly in case of increase from baseline grade 0 to 1
Increase from baseline grade 0 or 1 to grade 2 ( $> 3.0 - 5.0 \times \text{ULN}$ )	Dose interruption of ribociclib/placebo If resolved to $\leq$ baseline grade in $\leq 21$ days, then maintain dose level If resolved to $\leq$ baseline grade in $> 21$ days or toxicity recurs, then reduce 1 dose level Repeat liver enzyme and bilirubin tests twice weekly for 2 weeks after dose resumption If toxicity recurs after two dose reductions or recovery to $\leq$ baseline grade is $> 28$ days, discontinue ribociclib/placebo
Increase from baseline grade 0 or 1 to grade 3 ( $> 5.0 - 20.0 \times \text{ULN}$ )	Dose interruption of ribociclib/placebo until resolved to $\leq$ baseline grade, then lower 1 dose level of ribociclib/placebo  Repeat liver enzyme and bilirubin tests twice weekly for 2 weeks after dose resumption  If recovery to $\leq$ baseline grade is $> 28$ days, discontinue ribociclib/placebo If toxicity recurs, discontinue ribociclib/placebo
Increase from baseline grade 2 to grade 3 ( $> 5.0 - 20.0 \times \text{ULN}$ )	Dose interruption of ribociclib until resolved to $\leq$ baseline grade, then lower 1 dose level of ribociclib/placebo Repeat liver enzyme and bilirubin tests twice weekly for 2 weeks after dose resumption  If toxicity recurs after two dose reductions or recovery to $\leq$ baseline grade is $> 28$ days, discontinue ribociclib./placebo
Grade 4 ( $> 20.0 \times \text{ULN}$ )	Discontinue ribociclib/placebo
AST or ALT and concurrent Bilirubin	

For patients with normal ALT and AST and total bilirubin at baseline: AST or ALT > 3 x ULN combined with total bilirubin > 2 x ULN without evidence of cholestasis or For patient with elevated AST or ALT or total bilirubin at baseline: baseline : [AST or ALT >2 x baseline AND >3.0x ULN] OR [AST or ALT 8.0 x ULN]- whichever is lower- combined with [total bilirubin >2 x baseline AND >2.0 x ULN]
	
Discontinue ribociclib/placebo

Confounding factors and/or alternative causes for increased transaminases should be excluded before dose interruption/reduction. They include but are not limited to: concomitant medications, herbal preparations or dietary supplements, infection, hepato-biliary disorder or obstruction, new or progressive liver metastasis, and alcohol intake.
	

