- Aspartate transaminase (AST) <  $2.5 \times \text{ULN}$ , except for patients with liver metastasis, who are only included if the AST is <  $5 \times \text{ULN}$
- Alanine transaminase (ALT) <  $2.5 \times \text{ULN}$ , except for patients with liver metastasis, who are only included if the ALT is <  $5 \times \text{ULN}$
- Patient must have the following laboratory values within normal limits or corrected to within normal limits with supplements before the first dose of study medication:
  - Sodium
  - Potassium
  - Magnesium
  - Total Calcium (corrected for serum albumin)

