### 6.5.1.2.1 Additional follow-up for hepatic toxicities

Increase in transaminases combined with total bilirubin (TBIL) increase may be indicative of drug-induced liver injury (DILI), and should be considered as clinically important events. The threshold for potential DILI may depend on the patient's baseline AST/ALT and TBIL value; patients meeting any of the following criteria will require further follow-up as outlined below:

- For patients with normal ALT and AST and TBIL value at baseline: AST or ALT > 3.0 x ULN combined with TBIL > 2.0 x ULN
- For patients with elevated AST or ALT or TBIL value at baseline: [AST or ALT > 2 x baseline AND > 3.0 x ULN] OR [AST or ALT > 8.0 x ULN], whichever is lower, combined with [TBIL > 2 x baseline AND > 2.0 x ULN]

Medical review needs to ensure that liver test elevations are not caused by cholestasis, defined as: ALP elevation > 2.0 x ULN with R value < 2 in patients without bone metastasis, or elevation of ALP liver fraction in patients with bone metastasis.

[figure not shown]
Note: The R value is calculated by dividing the ALT by the ALP, using multiples of the ULN for both values. It denotes the relative pattern of ALT and/or ALP elevation is due to cholestatic or hepatocellular liver injury or mixed type injury.

In the absence of cholestasis, these patients must be immediately discontinued from study drug treatment, and repeat LFT testing as soon as possible, preferably within 48 hours from the awareness of the abnormal results. The evaluation should include laboratory tests, detailed history, physical assessment and the possibility of liver metastasis or new liver lesions, obstructions/compressions, etc.

Hepatic toxicity monitoring includes the following LFTs: albumin, ALT, AST, total bilirubin, direct and indirect bilirubin, alkaline phosphatase (fractionated if alkaline phosphatase is grade 2 or higher), creatine kinase, prothrombin time (PT)/INR and GGT. For patients with Gilbert Syndrome: total and direct bilirubin must be monitored, intensified monitoring applies to changes in direct bilirubin only.

Close observation is recommended in case of AST, ALT, and/or bilirubin increase requiring dose interruption, which involves:

- Repeating liver enzyme and serum bilirubin tests **two or three times weekly**. After dose resumption repeat liver enzyme and bilirubin tests twice weekly during the first 2 weeks,

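### Table 6-5's block headings drop some combined ALT/AST and bilirubin rises, leaving a weaker dose instruction or none

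*Protocol*

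**What the plan says.** Protocol Section 6.5.1.2, Table 6-5, has three blocks, each with its own entry condition.

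- **Bilirubin block**, headed "TOTAL BILIRUBIN without ALT/AST increase above baseline value". Grade 2 (above 1.5 and up to 3.0 x ULN): interrupt, with 21- and 28-day rules. Grade 3: interrupt and reduce; if recovery takes more than 28 "days or toxicity recurs, discontinue ribociclib /placebo". Grade 4: discontinue.
- **ALT/AST block**, headed "AST or ALT without bilirubin elevation" above 2 x ULN. Its first row covers "Same grade as baseline or increase from baseline grade 0 to grade 1", and the action is "No dose adjustment required with LFTs monitored per protocol if same grade as baseline", or bi-weekly after a rise from grade 0 to 1.
- **Combined block**: discontinue. With normal baseline it needs ALT or AST above 3 x ULN with bilirubin above 2 x ULN, without cholestasis. "For patient with elevated AST or ALT or total bilirubin at baseline", the ALT/AST limb needs more than 2 x baseline and more than 3 x ULN, or 8 x ULN, whichever is lower.

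Section 5.2 admits patients with ALT below 2.5 x ULN, "except for patients with liver metastasis, who are only included if the ALT is" below 5 x ULN. The AST limits are the same.

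Section 6.5.1.2.1 treats a transaminase rise combined with a bilirubin rise as clinically important. It then says: "Close observation is recommended in case of AST, ALT, and/or bilirubin increase requiring dose interruption".

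**The concern.** A liver-toxicity table should not give a milder instruction when a second marker worsens. Here it can, because each heading excludes patients whom no other block takes up. This runs against the protocol's own statement in Section 6.5.1.2.1 about combined rises.

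More than the interruption is at stake. Close observation is tied to an increase that requires interruption, so a patient moved to a row without interruption also loses that trigger. The text after Table 6-3 makes only the listed discontinuation events mandatory, so losing the bilirubin rows also loses their binding 28-day stop.

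The table is in use. Amendment 4 revised it, and Section 7.1 refers to it for monitoring liver abnormalities in its instructions on cross-over patients, who are newly exposed to ribociclib.

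**Working it through.** No sample-size or power figure is involved. The check applies the three entry conditions to each possible state.

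**Inputs.** Block headings and rows from Table 6-5. ALT/AST grades from the SAP's Appendix 1: grade 1 is above ULN to 3.0, grade 2 above 3.0 to 5.0, grade 3 above 5.0 to 20.0, grade 4 above 20.0 x ULN. Entry limits from Section 5.2.

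**Assumptions.** No cholestasis. The baseline value in the bilirubin heading is read as baseline grade, which favours the protocol. Read literally, any numerical ALT rise would exclude the bilirubin rows and the gaps would be wider.

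**Normal baseline: 5 ALT/AST grades x 4 bilirubin bands = 20 states.**

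| ALT/AST now | Bilirubin >1.5–2.0 | >2.0–3.0 | >3.0–10 | >10 (x ULN) |
|---|---|---|---|---|
| Grade 0 | interrupt, and no adjustment | interrupt | interrupt and reduce | discontinue |
| Grade 1 | no adjustment only | no row | no row | no row |
| Grade 2 | interrupt | discontinue | discontinue | discontinue |
| Grade 3 | interrupt and reduce | discontinue | discontinue | discontinue |
| Grade 4 | discontinue | discontinue | discontinue | discontinue |

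One state has two rows, one has only the weaker row, three have no row, and 15 (3 at grade 0, 12 at grades 2–4) are at least as strict as for bilirubin alone: 1 + 1 + 3 + 15 = 20.

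As an example of the inversion, take bilirubin 1.8 x ULN. With ALT at 2 x ULN the bilirubin heading excludes the patient, and the ALT/AST row asks for no adjustment.

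**Raised baseline, bilirubin above 2 x ULN.** For baseline ALT of B x ULN with B above 1 and below 2.5 (no liver metastases), the combined row needs ALT above both 2B and 3.0. Once ALT passes 3.0 (grade 2), both single-marker headings exclude the patient. ALT from above 3.0 up to 2B therefore matches no row:

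- B = 1.5 or less: 2B is at most 3.0, so there is no gap.
- B = 2.0: ALT above 3.0 and up to 4.0.
- B = 2.4: ALT above 3.0 and up to 4.8.

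Example: baseline 2.0, now 3.6, bilirubin 2.5 x ULN. ALT has risen from grade 1 to 2, bilirubin exceeds 2, and 3.6 is not above 4.0, so no row applies. At bilirubin 1.8 x ULN the ALT/AST row would say interrupt.

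With liver metastases: baseline 2.8, now 5.4 (grade 3), bilirubin 2.5 x ULN. The threshold is 2 x 2.8 = 5.6, which is not met, so no row applies. At bilirubin 1.9 x ULN the ALT/AST row requires interruption and a dose reduction.

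**Fallback, Table 6-8 against the bilirubin rows.** The first action is the same at grades 2, 3 and 4. At grade 2, Table 6-8 has no 21- or 28-day rule. At grade 3 it has no 28-day stop and discontinues only on recurrence at grade 3; Table 6-5 discontinues on any recurrence.

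**The case against.** The strongest reply is that no investigator is bound to continue dosing. Section 6.5.1.2 calls these recommendations and puts clinical judgment first, and Section 7.1.3 tells the investigator to stop treatment that is harming the patient. Section 6.5.1.2.1 points away from treating a combined rise as mild. Alternative causes must be excluded before interruption even for bilirubin alone. Table 6-8 interrupts at grade 2 and could be read as covering any hepatic event that Table 6-5 leaves out, including the inverted state. All of this stands as mitigation. But Table 6-8 is for other adverse reactions and is not named for hepatic events. In the inverted state a Table 6-5 row already applies and says something different.

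The two-row state is arguable. The tables manage drug-related reactions, and an unchanged ALT is not one, so a sensible reader would follow the bilirubin row. The text does not say so.

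A reader might infer that a missing precedence rule causes the inversion. It does not: only one row matches there, so the heading's scope is the cause. Precedence matters only in the two-row state.

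A reader might also want to count the liver tests lost. The documents do not support a firm figure. Two to three tests a week for four weeks gives 8 to 12, but only if drug is held throughout. The comparison is 2 if bi-weekly means every two weeks, or 8 if it means twice a week.

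**Conclusion.** Wrong as written: a minor-to-moderate patient-safety wording correction. On the reading kinder to the protocol, with normal baseline and no cholestasis, 4 of 20 states have a weaker instruction or none in Table 6-5, and a fifth arguably has two that conflict. Patients who enter with ALT/AST above 1.5 x ULN have a further gap above 3 x ULN. These are table states, not patients; the documents do not give the number affected.

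Two stronger inferences are not supported. The protocol does not forbid interruption in any of these states; the written default is weaker or unclear. Nor does the inverted state leave a patient who meets the protocol's criteria for potential drug-induced liver injury on drug, because bilirubin up to 2.0 x ULN with ALT/AST up to 3 x ULN is below those thresholds. No endpoint, power or alpha is affected.

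**What to change.** In Table 6-5, delete the limiting phrase from both headings: the condition on ALT/AST in the bilirubin heading and the condition on bilirubin in the ALT/AST heading. Then state that:

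1. the bilirubin rows and the ALT/AST rows each apply at any level of the other marker, unless the combined discontinuation row is met;
2. when rows from both blocks apply, the stricter action governs.

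Leave the exclusion of confounding factors and alternative causes as it is.

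Both phrases have to go. If only the bilirubin heading were changed, the patient with baseline ALT 2.8, now 5.4, and bilirubin 2.5 x ULN would get only the bilirubin grade 2 action (same dose on recovery within 21 days), while at bilirubin 1.9 x ULN the dose is reduced. With both changes, all 20 states are at least as strict as for either marker alone. The raised-baseline examples then get interruption (3.6 with 2.5 x ULN) and interruption with dose reduction (5.4 with 2.5 x ULN).

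The cost is table wording in an amendment or investigator letter. It adds no scheduled visits or data, and extra liver tests only for patients who would then be interrupted.
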